In addition, the number of days to resolution of the five aggregated symptoms will be compared based on the serum 25D level at Day 14 (<50 ng/mL vs 50 to 100 ng/mL and 50 to 100 ng/mL vs >100 ng/mL), regardless of the assigned treatment group. The comparison will be done using a Chi-square test. Frequency of relapses will be calculated, if possible, to account for potential worsening of symptoms after resolution (defined immediately above), with relapse being defined as achieving an aggregate FLU-PRO Plus[©] score >5 for a minimum of three consecutive days.

The following secondary endpoints will be tested statistically with methods described below, and the nominal p-value will be reported for evaluation:

- The number of days to resolution of five symptoms (trouble breathing, chest congestion, dry or hacking cough, body aches and pains, and chills and shivering), as measured by the FLU-PRO Plus[©] questionnaire, with resolution defined as the first aggregate symptom score of ≤5 which is maintained for a minimum of three consecutive days (see Section 5.2), with no individual symptom score >1;
- Resolution, defined as the first score of ≤5 which is maintained for a minimum of three consecutive days (without subsequent relapse), for the aggregate five COVID-19 symptoms (trouble breathing, chest congestion, dry or hacking cough, body aches and pains, and chills and shivering) and for each individual symptom, defined as a score of 0 or 1, as measured by the FLU-PRO Plus[©] questionnaire as of Day 10;
- 3. Incidence of emergency room/urgent care visits;

CTAP101 | CTAP101-CL-2014 | CTAP101-CL-2014 Protocol VV-TMF-183735 | Version 8.0 dated 16 Nov 2021

Protocol CTAP101-CL-2014	OPKO Pharmaceuticals, LLC
CTAP101 (calcifediol) Extended-release Capsules	Page 12 of 82

- 4. Incidence of oxygen saturation below 94% (without supplemental oxygen);
- 5. Incidence of hospitalizations (mean duration of hospitalization will also be presented);
- 6. Incidence of requirement for mechanical ventilation; and,
- 7. Mortality rate (as incidence).

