Endpoints listed will be summarized. For the analysis of individual symptoms in endpoint #2 above, the threshold of ≤ 1 is appropriate because it describes minor symptom severity (at worst "a little bit") which seems unlikely to presage a poor outcome. Analysis of the resolution of individual symptoms will be performed using a logistic regression, with baseline symptom score, baseline 25D level, and body weight as covariates. Analysis of the secondary endpoints based on incidence will be performed with a Chi-square test. Mean duration will be analyzed with analysis of covariance (ANCOVA). Mortality will be analyzed as incidence, with logistic regression with baseline symptom score, baseline 25D level and body weight as covariates. Rates only will be reported if there are too few deaths to be formally analyzed.

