The severity, duration and clinical course of COVID-19 illness will be compared between treatment groups by analyzing changes in quality-of-life assessments recorded on the FLU-PRO Plus[©] questionnaire. Five of the six items from the questionnaire to be analyzed are: "Overall, how severe were your infection symptoms today?", "Overall, how were your infection symptoms today compared to yesterday?", "How much did your infection symptoms interfere with your usual activities today?", "Have you returned to your usual activities today?", "In general, how would you rate your physical health today?", and "Have you returned to your usual health today?" The scores for: symptom severity range from 0 (no infection symptoms today) to 4 (very severe); symptoms today range from 1 (much better) to 7 (much worse); symptom interference range from 1 (not at all) to 5 (very much). The first of two consecutive scores of ≤ 1 spanning at least three days and no more than five days will be considered the day of resolution, provided that no intervening scores of >1 are recorded. The scores for return to usual activities or health are either "yes" or "no", and the first occurrence of "yes" will be deemed to be day of resolution provided that a second "yes" is recorded no more than 5 days later without an intervening "no". The remaining sixth item to be analyzed is: "physical health range from 1 (poor) to 5 (excellent). The first of two consecutive scores of >4 spanning at least three days and no more than five days will be considered the day of resolution, provided that no intervening scores of <4 are recorded. Each item will be compared between treatment groups using a Cox proportional hazards model with covariates (aggregate FLU-PRO Plus[©] score for the selected five COVID-19 symptoms at baseline, serum total 25D at baseline, and body weight).

The clinical course of COVID-19 will be examined by subgroups defined by serum total 25D levels <50 ng/mL, 50 to 100 ng/mL and >100 ng/mL at Days 7, 14, 21 and 28.

Inclusion Criteria

Each subject must meet the following criteria to be enrolled and randomized into one of the two treatment groups of this study:

1) Male or female ≥ 18 years of age;

- 2) Confirmed within the past 3 days to have SARS-CoV-2 infection as evidenced by a positive nasopharyngeal swab test using RT-PCR or any substitutable FDA-authorized diagnostic test;

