4.2 Inclusion Criteria

Each subject must meet the following criteria to be enrolled and randomized into one of the two treatment groups of this study:

- 1) Male or female ≥ 18 years of age;
- 2) Confirmed within the past 3 days to have SARS-CoV-2 infection as evidenced by a positive nasopharyngeal swab test using RT-PCR or any substitutable FDA-authorized diagnostic test;
- 3) Confirmed to have only mild or moderate COVID-19 based on the first of the patient reported scores obtained during screening which meets the criterion of a FLU-PRO Plus[©] score ≥ 1.5 for each of the chest/respiratory and body/systemic domains, and the absence of clinical signs indicative of more severe disease (eg, oxygen saturation < 94% on room air or respiration rate >30 bpm);
- 4) Represents on self-assessment that the current COVID-19 symptoms are not consistent with usual health and that they are the same or worse than on the previous day;
- 5) Willing to limit the use of vitD therapies or supplements except for normally fortified food products (eg, milk) during the course of the 6-week study;
- 6) Must demonstrate the ability to comply with all study requirements; and,
- 7) Must be without any disease state or physical condition that might impair evaluation of safety or which, in the investigator's opinion, would interfere with study participation.

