9.4 Determination of Sample Size

Primary outcome #1 (attainment of serum 25D levels at \geq 50 ng/mL): Assuming that no more than 25% of the control group will achieve an increase in serum 25D to \geq 50 ng/mL by Day 28 versus greater than 75% in the CTAP101 Capsules group, a sample size of 19 per group will provide 90% power at alpha 0.025 one sided for a Chi-square test of the two groups.

Primary outcome #2 (severity of illness by five symptoms): A sample size of 80 per group (total of 160) is planned. This will provide greater than 80% power at one sided alpha of 0.025 based on a log rank test assuming 50% of subjects in the control group and 70% of the CTAP101 Capsules group will have achieved resolution of symptoms by Day 28. This is based on an expected hazard ratio (of achieving resolution) of 1.74.

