4.3 Full Analysis Population

The full analysis set (FAS) or population is a subset of the ITT set from which subjects are excluded who did not receive any study drug or have a baseline aggregate five symptom score of >5. For the secondary analyses of individual symptom scores and quality-of-life responses, further subjects who do not have a baseline score of >1 for that symptom or response will be excluded.

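### The Cox models for three graded quality-of-life items (secondary endpoint 8) omit the item's own baseline score, which is already collected; adding it is a free gain in precision for a supportive analysis.

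*Protocol*

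**What the plan says.** The Protocol Synopsis (Statistical Analyses), Protocol 9.10.2 and SAP 6.10.2 give the same model for all six quality-of-life items: "Each item will be compared between treatment groups using a Cox proportional hazards model with covariates". The list is the five-symptom aggregate at baseline, then "serum total 25D at baseline, and body weight". The item's own baseline appears in none of the three places.

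The items differ in kind. Overall severity (0 to 4) and interference (1 to 5) resolve at a score of 1 or less. Physical health (1 to 5, 5 best) resolves above 4. The comparison with yesterday runs from 1 to 7. The two return-to-usual items are yes/no.

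On who is analysed, SAP 4.3 says "further subjects who do not have a baseline score of >1 for that symptom or response will be excluded"; Protocol 9.5 has the same rule. Protocol 9.1 and SAP 6.1 take as baseline the latest non-missing pre-dose value, preferably from Day 0.

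Elsewhere, the primary Cox model (Protocol 9.10.1, SAP 6.10.1) adjusts for the baseline of its own outcome, the aggregate. The individual-symptom logistic models are fitted "with baseline symptom score, baseline 25D level, and body weight as covariates".

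On status, "A sample size of 80 per group (total of 160) is planned" refers to primary outcome 2. No power or event count is given for endpoint 8. The Synopsis says of the listed secondary endpoints 1 to 7 that "the nominal p-value will be reported for evaluation"; endpoint 8 is not in that list.

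**The concern.** Time to an absolute threshold depends on how far from it a subject starts. On interference, a subject at 2 needs one step to resolve and a subject at 5 needs four. The planned models carry this information only through the five-symptom aggregate, which uses 5 of the 32 questionnaire items (Protocol 3.2) and is an imperfect stand-in for overall severity, interference or physical health.

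In a Cox model, leaving out a prognostic covariate lowers power when a treatment effect exists, even under perfect randomisation. It also gives a hazard ratio nearer 1 than the one conditional on that covariate, and chance imbalance in the item's baseline goes unadjusted. The plan already adjusts its primary model for the outcome's own baseline and gives no reason for doing otherwise here.

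**Working it through.** **1. Which items have a baseline worth adjusting for**

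| Item | Baselines left after the >1 rule | Own baseline useful? |
|---|---|---|
| Overall severity, 0–4 | 2, 3, 4 | Yes |
| Interference, 1–5 | 2, 3, 4, 5 | Yes |
| Physical health, 1–5 (5 best) | 2, 3, 4, 5 | Yes, once the rule is corrected |
| Compared with yesterday, 1–7 | Narrow | Little: a change rating, limited at screening |
| Usual activities; usual health (yes/no) | Rule undefined | No: constant if all start at no |

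The limit on the fourth row comes from inclusion criterion 4 (Protocol 4.2): "current COVID-19 symptoms are not consistent with usual health and that they are the same or worse than on the previous day". For physical health the >1 rule runs the wrong way. It drops the worst rating (1) and keeps subjects at 5, who already meet the resolution score.

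**2. The nearest stated power figure**

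Endpoint 8 has none. Protocol 9.4 gives more than 80% power for primary outcome 2 (one-sided 0.025, 50% versus 70% resolved by Day 28, HR 1.74).
- HR: ln(0.3)/ln(0.5) = 1.737, which agrees with 1.74.
- Day-28 events: 80 × (0.50 + 0.70) = 96. Schoenfeld power: Φ(√96 × ln 1.74 / 2 − 1.96) = Φ(0.75) = 77.4%.
- Day-42 events under constant hazards: 80 × (2 − 0.5^1.5 − 0.3^1.5) = 118.6, giving 85.4%.

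So the stated figure is reached with Day-42 but not Day-28 events. This only anchors the simulation; it says nothing for or against the present point.

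**3. Simulation at the planned size**

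From Protocol 9.4: 80 per arm, conditional HR 1.74, 50% of controls resolved by Day 28, one-sided 0.025. Assumed: exponential times; aggregate HR 1.3 per SD; a three-level item baseline; correlation 0.3, 0.6 or 0.8 between aggregate and latent item score; item baseline HR per SD as shown, given the aggregate. There were 2,000 runs per cell, so the Monte Carlo error is √(0.75 × 0.25/2,000), or about 1 point. Cells show power (%) for the planned model → with own baseline added, at correlations 0.3 / 0.6 / 0.8.

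| HR per SD | Censored at Day 28 | Gain | Censored at Day 42 | Gain |
|---|---|---|---|---|
| 1.0 | 75.8→76.1 / 76.0→75.7 / 76.5→76.2 | 0.3 / −0.3 / −0.3 | 85.0→84.9 / 84.1→84.1 / 83.0→82.8 | −0.1 / 0.0 / −0.2 |
| 1.25 | 75.2→76.6 / 73.9→75.3 / 75.4→75.4 | 1.4 / 1.4 / 0.0 | 82.8→83.6 / 83.3→84.0 / 84.5→85.0 | 0.8 / 0.7 / 0.5 |
| 1.5 | 69.3→74.0 / 70.9→74.4 / 72.8→75.5 | 4.7 / 3.5 / 2.7 | 77.7→83.7 / 80.5→84.6 / 81.4→83.6 | 6.0 / 4.1 / 2.2 |
| 2.0 | 60.1→73.8 / 63.3→75.7 / 66.5→74.0 | 13.7 / 12.4 / 7.5 | 65.9→80.6 / 67.7→80.6 / 73.1→81.6 | 14.7 / 12.9 / 8.5 |

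Average hazard ratio at Day 28, planned versus with own baseline: 1.74–1.76 versus 1.76–1.78 at 1.25 per SD; 1.70–1.74 versus 1.76–1.78 at 1.5; 1.61–1.67 versus 1.76–1.77 at 2.0.

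**4. A smaller effect and sample**

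Assumed: 73 per arm (0.92 × 80 = 73.6, from the blinded figure in SAP 5.2), placebo median 12 days, 42-day follow-up, HR 1.5, a three-level item with SD 0.7. Across repeat simulations with correlations 0.3 to 0.8, the gain was 0–2 points at 0.2 log hazard per item point, 1–4 at 0.4 and 1–10 at 0.6. For a four-level item at correlation 0.45, power rose from 59% to 64% at 0.4 and from 52% to 64% at 0.6.

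The two scales do not line up exactly. With SD 0.7, the strengths 0.2, 0.4 and 0.6 per point are exp(0.14) = 1.15, exp(0.28) = 1.32 and exp(0.42) = 1.52 per SD.

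**5. No treatment effect**

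In the section 3 set-up with true HR 1.0 (correlation 0.6, Day 28), both models average 0.99–1.00. Rejection is 3.5% versus 3.3% at 1.5 per SD and 2.8% versus 2.9% at 2.0, so the omission inflates nothing.

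**The case against.** The strongest reply is that the plan already adjusts for baseline severity through the aggregate, so the gain rests wholly on residual prognostic strength that no document states. That stands. At 1.0 per SD there is no gain, and at 1.25 it is at most 1.4 points. A high correlation between the aggregate and overall severity is plausible and shrinks the gain further.

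Three stronger readings are tempting, and the documents do not support them.
- A reader might infer that the planned hazard ratio is biased or the test invalid. The shift is non-collapsibility: the less-adjusted model targets a different hazard ratio. The estimand (Protocol 2.1.2, SAP 2.2) does not condition on an item's baseline, and nothing shifts under the null.
- A reader might infer that all six items are affected. The two that ask directly about return to usual activities and usual health gain nothing if everyone analysed starts at no.
- A reader might take the individual-symptom models as settled precedent. Own score is the natural reading there, but the same phrase is used for mortality, which has no symptom score of its own. The primary Cox model is the firmer comparison.

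Requiring a Day 0 score specifically could also drop subjects: the plan allows for a missing Day 0 value, and SAP 6.2 does not impute missing quality-of-life values. This bears on the wording of the fix, not on the point.

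**Conclusion.** The point holds for overall severity, interference and physical health, as a precision improvement to a supportive analysis with no stated power or alpha control. Its size is conditional. The loss is nil if the item's baseline adds nothing to the aggregate. It is about 0–2 points if weakly prognostic (1.25 per SD or 0.2 per point) and about 1–5 if moderately so (1.5 per SD or 0.4 per point; 6.0 in one Day-42 cell). If strongly prognostic (2.0 per SD or 0.6 per point) it is 1–10 or somewhat more, with 14.7 the most extreme cell.

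These figures rest on assumed prognostic strengths, correlations of 0.3–0.8 and constant hazards. They also ignore the further item-level exclusions in SAP 4.3. Adding the covariate costs essentially nothing when it is not prognostic, so the uncertainty about size does not argue against the change.

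**What to change.** Before unblinding, add one sentence to the Protocol Synopsis, Protocol 9.10.2 and SAP 6.10.2: for the overall-severity, interference and physical-health items, the Cox model also includes the item's own baseline score, taken by the existing rule in Protocol 9.1 and SAP 6.1. Keep the aggregate, baseline 25D and body weight. Leave the two yes/no items and the comparison with yesterday as they are.

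In the same edit to Protocol 9.5 and SAP 4.3, state the baseline inclusion rule for physical health in the right direction, so that it excludes subjects already at the resolution score and keeps those with the worst rating.

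The cost is a few lines of text and one model term for three items, with no new data. All places should carry the same wording, since the SAP supersedes where the two differ. Made before unblinding this is routine; made afterwards it could look data-driven.

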1 INTRODUCTION

1.1 Vitamin D Insufficiency

Calcifediol is 25-hydroxyvitamin D₃ (25D₃), the physiological precursor to the active vitamin D (vitD) hormone, 1,25-dihydroxyvitamin D₃ (calcitriol or 1,25D₃). This prohormone is synthesized by the liver from vitamin D₃ (cholecalciferol) generated endogenously in skin following exposure to sunlight or obtained from the diet or supplements. Another prohormone, 25-hydroxyvitamin D₂, is synthesized hepatically from vitamin D₂ (ergocalciferol), which cannot be produced endogenously but is obtained only from the diet or supplements. These two prohormones are collectively referred to as "25-hydroxyvitamin D (25D)". Unless an individual is receiving significant ergocalciferol supplementation, essentially all of the 25D in blood consists of calcifediol.

It is widely accepted that serum total 25D is the best indicator of a patient's vitD status. Serum total 25D levels of \geq 30 ng/mL are currently considered adequate while levels of <30 ng/mL are considered "insufficient" [Holick et al 2011]. The commonly used reference range for serum total 25D is 30 to 100 ng/mL [Souberbielle et al 2010]. Levels of serum total 25D in the general population vary according to many factors, including intensity of sunlight (varying with geographic location and season), exposure to sunlight (affected by skin pigmentation, use of sunscreen and other cultural factors), age and dietary intake [Holick 1995]. Levels tend to be lower during the winter and at higher latitudes. VitD deficiency (<20 ng/mL) in the US is most common in pigmented (decreased vitD production in skin) and obese (increased volume of distribution of vitD due to adiposity) subjects, the same population that appears to be most susceptible to infection with SARS-CoV-2.

Serum 25D levels above of 40-60 ng/mL have recently been recommended to reduce the risk of infection with severe acute respiratory syndrome 2 (SARS-CoV-2) and higher levels are thought to be useful for patients who become infected [Grant et al, 2020]. Serum levels of \geq 50 ng/mL have recently been shown to be required for 25D to modulate vitD-responsive endpoints in patients with chronic kidney disease (CKD), probably via activation by innate immune cells, extra-renal CYP27B1 [Strugnell et al, 2019]. It appears likely that similar high levels are required for 25D to be activated *in vivo* by CYP27B1 expressed in virus-stimulated macrophages.

1.2 Vitamin D and Viral Infections

Insufficient vitD has been linked to a large number of pathologies including immune disorders and infectious diseases. VitD functions as a key host defense regulator against viral pathogens. High levels of vitD has been associated with resistance to human immunodeficiency virus type 1 (HIV1) infection [Jimenez-Souza et al 2018]. Moreover, low levels of vitD have been associated with higher levels of immune activation and inflammation in HIV and other diseases [Jimenez-Souza et al 2018]. While the results of clinical trials studying vitD supplementation to reduce acute respiratory tract infections have differed, there are several well designed large metaanalyses that have supported vitD supplementation as being safe and protective against acute respiratory tract infections with individuals that were severely vitD deficient receiving the most benefit [Martineau et al 2017; Bergman et al 2013].

1.3 Vitamin D and Cathelicidin Gene

Despite extensive efforts to identify novel antimicrobials to address the treatment of patients with SARS-CoV-2 infection, little attention has been paid to endogenous human antimicrobial peptides, such as LL37, that can boost the host's immune response to the virus. Arguably the most effective, endogenous antimicrobial agent known to man, LL37 is the product of the endogenous human cathelicidin antimicrobial peptide (*CAMP*) gene and is secreted from monocyte/macrophages, dendritic cells and neutrophils in response to viral or bacterial infection [Nizet et al 2001]. Expression and secretion of LL37, along with numerous other endogenous antimicrobial activities, requires induction and priming. A key regulatory signal that can prime human macrophages for rapid and robust antimicrobial responses, including deployment of LL37 at the site of infection, is vitD, specifically calcifediol or 25D [Gombart et al 2009]. Like a loaded weapon with the safety left on, macrophages without sufficient serum total 25D as substrate are rendered unable to release LL37, and thus protect the host.

The innate immune response in antigen-presenting cells (monocyte/macrophages and dendritic cells) is initiated and perpetuated by pathogen-associated molecular patterns (PAMPs) derived from the cell wall and other unique signatures of the infecting virus interacting with pattern recognition receptors (eg, Toll-like receptors [TLR]). TLR activation eventually leads to upregulation of expression of the intracellular vitD receptor (VDR) and CYP27B1 (25D-1 α -hydroxylase); the latter event up-regulates generation the active vitD metabolite, 1,25-dihydroxyvitamin D (1,25D). That 1,25D can then engage the VDR in an intracrine mode and controls *CAMP* and interleukin 1 β (IL-1 β) gene expression; IL-1 β is a central initiator of the adaptive immune response.

Using upregulated expression of the potent endogenous antimicrobial *CAMP* mRNA by primary cultures of human monocyte/macrophages as an *ex vivo* read-out, extensive recent work [Rosen et al 2012; Liu et al 2006; Adams et al 2007; Krutzik et al 2008; Liu et al 2009; Edfeldt et al 2010; Fabri et al 2011; Montoya et al 2014; Chun et al 2014; Srikanth et al 2016] shows that insufficient serum levels of 25D (VDI) in the host induces an immune-compromised state. An insufficient level of 25D in human serum causes inadequate i) intracellular generation of 1,25D, ii) activation of the VDR, iii) transactivation of the *CAMP* gene and iv) production and release of LL37 to combat microbial invasion of the host. The end result is innate and subsequent adaptive immune deficiency.

Raising serum total 25D to sufficiently high levels can resolve the immune-compromised state in the human host. Accomplishing this with vitD supplements is unreliable and is difficult in obesity owing to the increased volume of distribution of the non-polar vitamin. In contrast, treatment with the more polar and extended-release calcifediol (Rayaldee or CTAP101 Capsules) is reliable and, depending on the administered dose, can take as little as 9-12 hours. Treatment with CTAP101 Capsules has been shown to be safe for administration to patients with stage 3 or 4 CKD, as evidenced by United States (US) Food and Drug Administration (FDA) approval of the product in 2016 as Rayaldee[®] (calcifediol) Extended-release Capsules.

Accumulating data suggest that hyperactive immune response to COVID-19 poses unique risks to the cardiovascular system and plays a role in disease severity. As the disease progresses, a concomitant rise in inflammatory cytokine levels may drive the depletion and exhaustion of T cell populations [Diao et al 2020]. On the other hand, vitD is an immune-modulating agent and has been implicated in the pathophysiology of autoimmune diseases, including systemic lupus

erythematosus and multiple sclerosis. VDI is a risk factor for multiple sclerosis and correlates with the disease severity. Thus,

appropriate treatment with Rayaldee may help to mitigate an overactive, adaptive T- and B-lymphocyte immune system response to the virus and ameliorate immune cell exhaustion [Adams et al 2007; Rosen et al 2012].

